Official title: Effects of CPAP on Diet, Physical Activity, and Cardiovascular Risk

NCT #: NCT01944020

Date of Document: September 29, 2017

Specific Aims:

Obstructive sleep apnea (OSA) has a variety of adverse cardiometabolic consequences. This disorder is characterized by recurrent episodes of partial or complete loss of airflow during sleep, resulting in low blood oxygen levels, frequent nocturnal arousals, and sleep architecture disruption. The associated daytime hypersomnolence experienced by some can lead to reduced physical activity and exercise. Estimated prevalence of OSA is as high 28% of the population (1), and the clinical entity "OSA syndrome" (OSAS), defined as OSA in conjunction with excessive daytime sleepiness is estimated to occur in as much as 1 of 20 adults (1). Almost all cross-sectional clinic-based studies as well as population-based observational studies have found an association between excess body weight and OSA, and it was reported that 70% of OSA patients are overweight or obese (2). Increased weight gain and BMI are associated with increased odds of OSA. This is critical, since the overall prevalence of overweight and obesity is ~68% and 34%, respectively, in the U.S (3). As such, there is a large proportion of the US population at risk of OSAS and its co-morbidities.

Whether obesity is strictly a cause of OSAS, or if a bidirectional relationship exists between obesity and OSAS has recently come into question (4). Newly diagnosed patients have a greater propensity for recent weight gain compared to controls (5). Metabolic, hormonal, and/or behavioral changes associated with OSAS may place patients in a condition favoring positive energy balance, which can lead to further weight gain or difficulty losing weight. Continuous positive airway pressure (CPAP) is effective in alleviating breathing and sleep abnormalities in OSAS, although it is unclear whether these improvements lead to weight loss. The proposed study will look closely at energy expenditure (EE) and energy intake (EI) with OSAS treatment to determine how CPAP affects these parameters. This will help determine if CPAP can improve weight control in obese OSAS patients, and if it can be used to promote weight loss and ameliorate obesity-related co-morbidities.

The proposal is to investigate the effects of 2 mo of CPAP on EE and EI in obese patients with OSAS. The proposal is a combined ambulatory and laboratory-based study. Free-living measures of physical activity (via waist-actigraphy), food intake (via 3-d food log), sampling of blood for appetite-regulating hormones (leptin, ghrelin, adiponectin, glucagon-like peptide-1 [GLP-1]), lipid profile, and inflammatory markers, and body composition measurements will be obtained at baseline and after 2 mo of CPAP treatment. At the start and conclusion of each treatment phase, patients will enter the laboratory for measures of polysomnographic sleep, hunger levels, and food intake (via ad libitum test meals). The objective of the proposed study is to determine how CPAP treatment affects energy balance in obese OSAS patients. The central hypothesis is that CPAP treatment will improve sleep architecture, which will be associated with improved EE, EI, cardiovascular health, and body composition. We have shown that adverse changes in sleep are associated with alterations in both EE and EI (6, 7). Specifically, reduced sleep duration is associated with increased nocturnal and 24-h EE (6). Moreover, we observed that rapid eye movement (REM) sleep is inversely related to hunger, and that both REM sleep and slow wave sleep (SWS) are inversely related to intake of fat and carbohydrate (7).

Aim 1 (Cardiovascular health): To determine the effects of 2 mo of CPAP compared to pretreatment baseline on body composition in obese OSAS patients.

Hypothesis 1: CPAP will reduce blood pressure, fasting glucose, total cholesterol, inflammatory markers, and percent body fat relative to baseline.

Aim 2 (Energy intake): To determine the effects of 2 mo of CPAP compared to pre-treatment baseline on hunger, food intake, and the hormonal regulation of food intake in obese OSAS patients.

Hypothesis 2: Hunger levels and ad libitum food intake will be lower in patients after CPAP vs. baseline.

Hypothesis 43: Abnormally high leptin levels will be reduced in CPAP vs. baseline. Levels of ghrelin (hunger signal) will be reduced, and glucagon-like peptide-1 (GLP-1; satiety signal) increased, after CPAP vs. baseline.

Research Strategy

Significance

Importance of the problem to public health: Obstructive sleep apnea (OSA) is a disorder characterized by recurrent episodes of partial or complete loss of airflow during sleep, due to narrowing or closure of the upper airway. The prevalence of OSA is stated to be as high as 28% of the population (1). This is critical, since there are many cardiometabolic consequences of sleep-disordered breathing-related hypoxia, including hypertension (8), coronary artery disease (9), stroke (1), systemic inflammation (2), dyslipidemia (10), insulin resistance (2), and increased overall mortality (11). Upper airway collapse results in repeated arousals during the night and fragmentation of sleep, and subsequently, significant reductions in slow wave sleep (SWS) and rapid eye movement (REM) sleep are observed in OSA patients (12). A consequence of these reductions in restorative sleep is excessive daytime sleepiness (EDS), which, when present with OSA, defines the clinical entity OSA syndrome (OSAS). OSAS is estimated to occur in up to 5% of the adult population, with another 5% having undiagnosed OSAS (1).

Obesity is considered a leading risk factor for the development of OSA. Indeed, ~70% of OSA patients are obese, and OSA occurs in ~45% of obese individuals (2). Rising rates of overweight and obesity suggest that OSAS prevalence will also be on the rise in the near future. An improved understanding of how OSA and its treatment affect energy balance is therefore important from a global public health perspective.

Obesity is mainly the result of an imbalance between energy intake (EI) and energy expenditure (EE), wherein EI is increased relative to EE, or EE is reduced relative to EI. Interestingly, not only is obesity a risk factor for OSA development, but OSA itself seems to play a role in further weight gain (4). It has been reported that newly diagnosed OSA patients have a history of

significant weight gain over the year prior to diagnosis (5), and the presence of OSA attenuates the effects of a weight loss intervention otherwise effective in non-OSA obese controls (13). Reasons for this are still uncertain, but OSA may predispose to positive energy balance. In terms of EE, EDS in OSAS is associated with reduced daytime physical activity (PA) (14). Conversely, increased 24-h EE has been reported in patients vs. controls (15). While it may seem that the increase in daily EE would prevent the development of a positive energy balance in OSA, it was proposed that the metabolic costs of sleep disruption are likely to trigger a set of compensatory neuroendocrine adaptations aimed at increasing hunger, reducing satiety, and stimulating food intake (16). In this way, it is possible that increased EE is overcompensated for by increased food intake. Indeed, evidence suggests a dysregulation of appetite-regulating hormones in OSA. Abnormally high levels of leptin (satiety signal) have been documented in OSA, suggesting a leptin resistance to levels beyond what is already seen in obesity (17). The appetite-stimulatory hormone ghrelin is also observed to be higher in OSA patients compared to non-OSA obese controls (17), suggesting that high EI may be present in OSA patients. EI has not been systematically studied in OSAS, but severity of sleep-disordered breathing was associated with increased preference for calorie-rich foods high in fat and carbohydrate in children (18).

The gold standard in OSA treatment is continuous positive airway pressure (CPAP). CPAP applies mild pressure through a nose mask to prevent occlusion of the upper airway during sleep (19). Clinical studies in OSA have demonstrated improvements in a variety of outcomes in response to CPAP. By eliminating recurrent episodes of nocturnal hypoxia, CPAP reduces sleep fragmentation and arousals (12) and increases the expression of SWS and REM sleep (15, 20). Daytime hypersomnolence is also alleviated by CPAP (21). An effect on some energy balance-related parameters has also been demonstrated, as CPAP was shown to reduce sleeping EE (15), and to normalize leptin and ghrelin to levels seen in obese non-OSA controls (17). This suggests that treating OSAS with CPAP may lead to improvements in appetite and food intake. Whether long-term CPAP treatment results in weight loss in obese OSA patients is still unclear, as weight loss has been shown to occur in some (22-24), but not other CPAP intervention studies (25-27).

Ramifications of proposed study for public health: Results of the proposed study will determine how CPAP treatment in obese OSAS patients affects energy expenditure and intake, as well as body composition and cardiovascular health. This information is significant because it will clarify the factors which contribute to the increased propensity for weight gain and cardiovascular disease in these patients, as well as determining which aspects of energy balance regulation are improved by CPAP treatment. CPAP is considered the first-line treatment for OSAS, and weight loss has also been promoted as the best nonmedical method for reducing the symptoms and overall prevalence of this disorder (1). Understanding how the components of energy balance and cardiovascular risk are affected by CPAP will allow practitioners and clinicians to more efficiently guide overall treatment approaches to optimize weight loss and symptom amelioration in these patients. This could include efforts to promote weight loss and improve respiratory function, sleep quality, and daytime functioning in this population by promoting CPAP in conjunction with other weight loss approaches to encourage optimal outcomes.

Research Design:

Study participants: Men and women, age 18-65 y, will be included in the study. Participants will be overweight, with a BMI \geq 25 kg/m2. However, in order to exclude patients who are at the highest risk patients with an AHI > 50 will be excluded from participation (45). Patients will not currently, or have previously been treated with CPAP. Once a diagnosis of OSAS is made and a CPAP prescription is given, but before the start of CPAP treatment, we will meet with potential participants to inform them of the study details. Those interested will begin the screening phase, followed by enrollment if they are eligible and interested in participation. A second group of participants who are diagnosed with OSA but do not choose to undergo CPAP will be studied, as a control group.

Participants will be excluded if they are currently taking any anti-psychotic medications, or hypnotics and other drugs to treat insomnia. Individuals with uncontrolled severe (stage 2) hypertension (blood pressure > 160/100 mmHg) or anemia will be excluded. Participants with uncontrolled severe hypertension will be considered as individuals with known severe hypertension who are not actively receiving medical or drug treatment to manage this disorder. Anemia will be defined from medical history. Habitual drivers, commercial drivers and individuals with any recent near-miss or prior car crashes due to excessive daytime sleepiness (i.e. high-risk drivers) will be excluded. Premenopausal women will be studied in the laboratory during the follicular phase of their menstrual cycle, to exclude the possible confounding effects of sex hormones on outcome parameters like sleep, EE, hunger, and food intake. Participants will be excluded if they have a history of coronary artery disease, transient ischemic attack, or stroke.

Study Design Overview: This study will investigate the effects of CPAP on EE and EI in obese patients with moderate-to-severe OSA and EDS. Following pre-experimental baseline measures, including a 1-d inpatient testing period at the CTSA at Columbia University Medical Center, participants will be instructed to use CPAP at home each night throughout the 2 mo treatment phases. After the 2 mo treatment phase, participants will undergo a repeat of baseline procedures including assessments and the 1-d inpatient testing period. Procedures for the non-CPAP control participants will be the same, with the exception that they will not be using CPAP during the 2-mo period.

Experimental Procedures: Anthropometric measures including height, weight, neck- and waist circumferences, and body composition via air displacement plethysmography will be taken at baseline before the start of CPAP treatment. A urine pregnancy test to confirm the absence of pregnancy will be administered to female participants before scanning. Height and weight will be used to calculate BMI. In addition, a baseline fasting blood sample of 12 ml will be obtained to assay for levels of appetite-regulating hormones (leptin, ghrelin, GLP-1), lipid profile, fasting glucose, and inflammatory markers (c-reactive protein [CRP], tumor necrosis factor- α [TNF- α], interleukin-6 [IL-6]). Blood pressure will also be measured at this time via sphygmomanometer. Questionnaires filled out during this baseline period will include the ESS, a questionnaire measuring daytime sleepiness (50), and the Functional Outcomes of Sleep Questionnaire (FOSQ), to assess quality of life in disorders of excessive sleepiness (51). The ESS is an

established metric that asks patients to rate their chances of dozing/falling asleep in 8 different situations. A score > 10 is indicative of pathological sleepiness, and the measure has frequently been used to characterize EDS in OSAS sufferers. The FOSQ is a 30-item questionnaire addressing the impact of sleepiness on multiple everyday activities (51). Ambulatory measures of PA, food intake, and sleep will be taken during a baseline 1-wk period before the start of the intervention. Free-living PA will be measured with a waist-mounted accelerometer (ActiLife 5, ActiGraph, Pensacola, FL) (52). A sleep-wake log will be filled out daily for 1 wk, for subjective estimates of sleep continuity measures, including total sleep time (TST), sleep efficiency (SE), and sleep onset latency (SOL). Patients will be asked to wear the accelerometer on their wrist at night, to provide objective measures of sleep quality and continuity (53), including TST, SE, and SOL. Food intake will be measured with a 3-d food log (54), filled out on 2 weekdays and 1 weekend day.

During the baseline assessment before treatment, patients will enter the laboratory at the CTSA at Columbia University for a 1-d period. Patients will arrive at ~0900 h and will remain in the laboratory for the following 24h. Patients will fill out questionnaires assessing their level of sleepiness during their wake episode throughout the laboratory day. A Likert scale will assess current energy level each hour spent awake ("How energetic do you feel right now?"; "How sluggish do you feel right now?") and a Likert scale will assess current feelings of hunger ("How hungry do you feel right now?"), satiety ("How satisfied do you feel right now?"; "How full do you feel right now?"), and appetite/food preferences ("How much would you like to eat something sweet right now?"; ("How much would you like to eat something salty right now?"; ("How much would you like to eat something savory right now?"; How much would you like to eat fruits/vegetables right now?").

Ad libitum EI will be measured during the laboratory day for each treatment phase. During the laboratory day, participants will self-select their food intake. Participants will have access to a specified food budget for the day (up to \$55.50) to purchase foods and beverages of their choice. Participants will be escorted by study personnel to local markets where they will be able to purchase foods they want to eat during the day. Participants will also have the opportunity to purchase food from take-out restaurants throughout the day. The only restrictions that will be imposed are that nutrient information must be available for the items purchased and that beverages must be nonalcoholic. Participants will not be able to keep any food not consumed during the experimental day. Participants will not be allowed to take any purchased foods home with them. Energy and macronutrient intakes will be calculated using Diet Analysis Plus Software using the weight (pre – post intake) and nutritional information of the food consumed.

Patients will have a fixed sleep episode from 2300-0700 h during the in-laboratory testing day, which will be identical in both phases. At the baseline visit, no CPAP will be used during the sleep episode. At the 2-mo post-treatment follow-up, CPAP will be used. Overnight sleep will be recorded via PSG during the sleep episode in the laboratory using a portable sleep system. The recording montage will include electroencephalogram, electrooculogram, electromyogram, electrocardiogram, nasal and oral airflow via thermistor, and oxygen saturation via pulse oximetry, and 30-sec epochs of sleep will be scored for sleep staging (Stage 1, Stage 2, SWS,

REM sleep), wakefulness, arousals, and respiratory events according to standard criteria (67). Patients will be discharged after awakening from the laboratory sleep episode.

Upon completion of the baseline 1-d inpatient visit, patients will return home for the 2 mo treatment phase where they will be using CPAP each night. Patients will be instructed to begin to CPAP at home each night throughout the 2 mo treatment phases. Nightly duration of CPAP use will be objectively monitored with a memory chip, and compliance will be defined as the use of the CPAP machine for at least 4 h/night for \geq 70% of the nights (i.e. 64 nights) (55). Participants will also complete a daily CPAP compliance form, in which they will document the duration of CPAP use for the prior night. We will also do random checks of compliance during the 2 mo period. Only compliant patients will undergo the in-lab testing at the end of the intervention period. During the final week of the intervention phase, free-living ambulatory measures of PA (waist-actigraphy), food intake (3-d food log), and subjective (sleep-wake log) and objective (wrist-actigraphy) sleep will be taken, as described above. In-lab testing will be done with the CPAP equipment. At the conclusion of the 2-mo treatment phase, all study procedures and measurements will be repeated. This will include questionnaires, fasting blood sample, anthropometry including BodPod, and the 1-d inpatient period. Procedures for the non-CPAP patients will be same during ambulatory and lab visits. The non-CPAP patients will not use any CPAP during the intervening 2-mo period.

Statistical Procedures:

Sample size estimates are for paired-samples, two-tailed level of significance at 0.05 and 80% power, and are based on prior studies showing a significant effect of CPAP vs. baseline on outcomes of interest. We hypothesize that reduced sleepiness in response to active CPAP treatment will result in increased free-living PA compared to sham. We expect to be able to detect an effect size of 1.195 for decreased Stanford Sleepiness Scores (37) with 8 patients. The main outcomes hunger and EI, have not previously been investigated in response to CPAP. However, we have previously demonstrated a relationship between REM sleep and SWS with hunger and food intake (7). We expect to be able to detect an effect size of 1.01 for REM sleep increases (43) and 1.64 for SWS increases (43) with 10 and 6 patients, respectively. We expect to be able to detect an effect size of 0.736 for decreased leptin with 17 patients (62). To have power to detect changes in leptin, we will recruit 25 patients, assuming a 30% drop-out rate.

Change-from-baseline will be calculated for single-measure parameters that are assessed at the pre-experimental baseline, and after the 2-mo experimental phase (including ESS, FOSQ, PA, blood samples, body composition, blood pressure). Paired-samples t-tests will be used to compare single-measure parameters that are assessed during laboratory phase 1 and laboratory phase 2. These will include polysomnographic sleep measures (sleep stages and indices of sleep-disordered breathing), and total energy and macronutrient intakes. Repeated or continuously measured parameters taken during laboratory phase 1 and laboratory phase 2 will be analyzed with two-way repeated measures ANOVA (factors: condition x time). These will include hourly measures of sleepiness (SSS), and appetite-satiety ratings. Non-parametric equivalent tests will be used if data are deemed to be not normally distributed. Significance will be set at p<0.05.

References:

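### The planned non-CPAP control group has no stated contrast or number; laboratory energy intake is tested pre-post only, and hunger most likely so

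*Combined protocol and SAP*

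**What the plan says.** Research Design, Study participants, adds a comparison group: "A second group of participants who are diagnosed with OSA but do not choose to undergo CPAP will be studied, as a control group". Study Design Overview and Experimental Procedures give these patients the same assessments and laboratory days, without CPAP.

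Statistical Procedures does not mention them. Its sample size basis is: "Sample size estimates are for paired-samples, two-tailed level of significance at 0.05 and 80% power". The leptin calculation (effect size 0.736, 17 patients, 30% drop-out) sets recruitment at 25. On the lead endpoints it says: "The main outcomes hunger and EI, have not previously been investigated in response to CPAP". No effect size or SD is given for either.

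The planned analyses fall into three classes:

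- **Laboratory single measures.** "Paired-samples t-tests will be used to compare single-measure parameters that are assessed during laboratory phase 1 and laboratory phase 2". The members of this class are listed: "These will include polysomnographic sleep measures (sleep stages and indices of sleep-disordered breathing), and total energy and macronutrient intakes".
- **Hourly laboratory ratings.** These "will be analyzed with two-way repeated measures ANOVA (factors: condition x time"). The members are again listed: "These will include hourly measures of sleepiness (SSS), and appetite-satiety ratings". The factor called condition is not defined.
- **Change-from-baseline measures.** "Change-from-baseline will be calculated for single-measure parameters that are assessed at the pre-experimental baseline" and again after 2 months. The examples are ESS, FOSQ, physical activity, blood samples, body composition and blood pressure. No test is named.

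Intake from the 3-day food log is assigned no analysis by name. The aims and hypotheses under Specific Aims compare CPAP with pre-treatment baseline only. The only other comparator in Statistical Procedures is sham CPAP, for physical activity, and the design has no sham arm.

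**The concern.** A control group is normally studied to show what happens without the treatment. Here it is measured in full, but the plan does not say how its data enter any analysis or how many controls are wanted.

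This matters most for laboratory EI. Participants choose their own food on an escorted, budgeted shopping day, and the second such day is no longer new to them. A change between the two days could reflect CPAP, two months passing, or familiarity with the procedure, and a paired test cannot tell these apart. The Significance section nevertheless says that the results will establish how CPAP affects energy intake, energy expenditure and the other outcomes.

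The controls are the only means in this design of seeing change without CPAP. With their use unstated, whether and how to compare the groups can be decided after the data are seen.

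**Working it through.** **Inputs from Statistical Procedures.** Two-sided 0.05, 80% power, paired samples; effect sizes and patient numbers of 0.736 (leptin, 17), 1.195 (sleepiness, 8), 1.01 (REM, 10) and 1.64 (SWS, 6); 30% drop-out; 25 recruited.

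**Assumptions, not in the documents.** The drift sizes; 17 evaluable controls; equal SDs of change in both groups; and, for laboratory outcomes, that the 30% drop-out also covers patients removed by the compliance rule.

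**Step 1. Reproduce the plan's figures.** For a one-group paired t-test, power comes from the noncentral t distribution with n − 1 degrees of freedom and noncentrality d√n.

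- Leptin: 0.736 × √17 = 3.03, power 81.3%. At n = 16 it is 78.6%, so 17 is the smallest adequate number.
- Sleepiness, n = 8: 82.5%. REM, n = 10: 81.1%. SWS, n = 6: 89.0%.
- Drop-out: 17/0.7 = 24.3, rounded up to 25.

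Every stated number reproduces as a one-group paired calculation. One pre-post group uses the whole figure of 25, and no number is left for controls.

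**Step 2. Paired test with drift and no CPAP effect, n = 17.** The noncentrality is drift × √17, with drift in SDs of change.

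| Drift | Noncentrality | Significant results |
|---|---|---|
| 0.1 | 0.41 | 7% |
| 0.2 | 0.82 | 12% |
| 0.3 | 1.24 | 21% |
| 0.5 | 2.06 | 49% |

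**Step 3. What the stated sample size gives between groups.** For a two-sample t-test of change at 17 v 17, the noncentrality is d/√(2/17), with 32 degrees of freedom.

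- Leptin, taking 0.736 as the full CPAP-minus-control difference: 0.736/0.343 = 2.15, power 55%. Reaching 80% needs 30 evaluable per group; 30/0.7 = 42.9, so 43 recruited per group.
- EI and hunger, which have no stated effect: the difference detectable at 80% power is 0.99 SD of change at 17 v 17, against 0.72 SD for the paired test at n = 17.

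**Step 4. Precision.** The 95% half-width is 2.120/√17 = 0.51 SD of change for the paired estimate and 2.037 × √(2/17) = 0.70 SD for the group difference at 17 v 17.

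**Step 5. When the control contrast itself misleads.** If drift is equal in both groups it cancels, and the two-sample test keeps its 5% error rate. If drift differs by 0.3 or 0.5 SD with no CPAP effect, the noncentrality at 17 v 17 is 0.87 or 1.46, and the test rejects 14% or 29% of the time.

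**The case against.** Every aim and hypothesis is worded as CPAP against baseline, so the paired tests and the paired sample size answer the questions asked. The sentence in Significance is a statement of public health relevance, not an inferential claim. The controls chose not to use CPAP. They are described as having OSA, whereas the CPAP recruits have an OSAS diagnosis, which by the protocol's own definition includes excessive sleepiness. Follow-up laboratory testing is limited to compliant CPAP users. Common drift is therefore not assured, and Step 5 shows what follows if it fails. No drift size is documented, and small drift does little harm.

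Much of this stands. The paired tests should stay, and the control contrast can only qualify them. What does not stand is leaving the group without any stated role: its weaknesses are a reason to fix and caveat the comparison in advance.

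Three stronger readings are tempting but unsupported:

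- **That no outcome has a group comparison.** For the change-from-baseline measures no test is named, so a comparison is neither stated nor excluded. The pre-post-only finding is firm for laboratory EI, not for food-log intake. For hunger it is an inference, because condition could mean CPAP against no CPAP.
- **That the 25 is shared with the controls, so that the paired test is underpowered.** The figure is 17/0.7 for one paired group and is tied to leptin. The natural reading is that it excludes controls, whose number is simply not given.
- **That the sample size is wrong.** It is correct for the test it describes.

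**Conclusion.** The point holds and should be fixed. The text is clear that a control group is planned with full procedures and that the analysis section gives it neither a contrast nor a number. No redaction or break in the text explains the omission. Followed as written, the plan leaves any CPAP effect on laboratory EI inseparable from time and repeat-visit effects, and most likely does the same for hunger.

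How much this matters depends on a drift that the documents do not give. On the figures in Step 2 the effect is minor at 0.1 SD of change and substantial at 0.3 SD or more. The stated 80% power does not extend to a control contrast. The 55% for leptin rests on treating a paired effect size as the full between-group difference, and for EI and hunger only a detectable difference can be given. The omission itself depends on none of these assumptions.

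A reader might also infer that adding the control comparison would establish causation. It would not: the groups are self-selected, and for laboratory outcomes one is filtered by compliance.

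**What to change.** In Statistical Procedures:

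1. Keep the paired tests as the primary analysis for the stated aims. Name the test for the change-from-baseline outcomes, assign an analysis to food-log intake, and define condition in the ANOVA.
2. Pre-specify a supporting between-group comparison with the controls, for laboratory EI and hunger first: group difference in change for single measures, and group by phase in a mixed model for hourly ratings. Add an ANCOVA of the 2-month value on group and baseline value as a sensitivity analysis.
3. Report this contrast beside any pre-post change attributed to CPAP. Describe it as non-randomised, limited to compliant CPAP users for laboratory outcomes, affected by the OSA/OSAS difference in recruitment, and valid only if drift is similar in both groups. Report how many patients the compliance rule removed.
4. State the planned number of controls, and that the 25 and the 80% power apply only to the paired test within the CPAP group.
5. Reconcile the reference to sham with a design that has no sham arm.

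The cost is about one paragraph and a few models on data already planned for collection. The drawbacks are a wider interval for the group difference than for the paired change (Step 4), more tests, and confounding that adjustment will not fully remove.

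### The follicular-phase rule is worded for the laboratory day only: the food log and home sleep measures fall outside it, and blood, blood pressure and body composition have no stated cycle phase

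*Combined protocol and SAP*

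**What the plan says.** Research Design, Study participants: "Premenopausal women will be studied in the laboratory during the follicular phase of their menstrual cycle", with the stated purpose "to exclude the possible confounding effects of sex hormones on outcome parameters like sleep, EE, hunger, and food intake".

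Experimental Procedures describes the other baseline collections without reference to cycle phase:
- Blood: "a baseline fasting blood sample of 12 ml will be obtained to assay for levels of appetite-regulating hormones".
- Blood pressure, tied to the blood sample: "Blood pressure will also be measured at this time via sphygmomanometer".
- Body composition: "body composition via air displacement plethysmography will be taken at baseline before the start of CPAP treatment".
- Activity, the 3-day food log and home sleep: a free-living week before the intervention, repeated in its final week.

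For follow-up the same section says: "At the conclusion of the 2-mo treatment phase, all study procedures and measurements will be repeated". It gives no day count and no visit window.

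Statistical Procedures puts one set of variables ("including ESS, FOSQ, PA, blood samples, body composition, blood pressure") under the pre-experimental baseline and the end of the 2-month phase. Polysomnography, laboratory intake and hourly ratings are put under laboratory phases 1 and 2. The recruitment target rests on a blood measure: "To have power to detect changes in leptin, we will recruit 25 patients, assuming a 30% drop-out rate".

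**The concern.** The protocol names sex hormones as a confounder, then controls for them in only part of the data they could affect. Food intake and sleep are each measured twice over, in the laboratory and at home, and only the laboratory version is protected. Leptin, ghrelin and GLP-1 are measured because they regulate appetite, so the protocol's reasoning about hunger and intake extends naturally to them, yet no phase is set for the blood sample.

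The main comparisons are within-person changes. If a woman's two samples come from different phases, any phase difference becomes part of her change score. With about 17 evaluable patients, a few such scores could matter. The plan does not ask for cycle day to be recorded, so nobody could check afterwards.

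A second, smaller matter is that a nominal 2-month follow-up and a follicular follow-up visit are not always the same day, and the plan does not say how to reconcile them.

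**Working it through.** **1. The plan's own figure.** For a paired t-test, two-sided alpha 0.05, 80% power and effect size 0.736 (Statistical Procedures), the noncentral t gives n = 17, with power 0.813. Allowing for 30% drop-out, 17/0.70 = 24.3, rounded up to 25. Both stated numbers reproduce, and nothing below changes them.

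**2. What the rule covers.**

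| Measure | Where or when taken | Phase rule stated? |
|---|---|---|
| Polysomnography, laboratory intake, hourly ratings | Laboratory day | Yes |
| 3-day food log, home sleep, activity | Free-living week before the intervention and its final week | No; outside the laboratory |
| Blood, blood pressure, body composition | Baseline and end of treatment; relation to the laboratory day not stated | No |

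Three places list items in the last row apart from the laboratory measures. The overview in Specific Aims groups blood and body composition with the free-living measures. The follow-up list in Experimental Procedures names the blood sample, the BodPod and the inpatient day as separate items. Statistical Procedures makes the split quoted above. On the other side, Study Design Overview counts the inpatient day among the pre-experimental baseline measures. Same-day collection is therefore possible but not required.

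**3. Follow-up timing.** Assumptions not in the documents: luteal phase of 14 days, so follicular days are 1 to L − 14 for cycle length L; baseline day d uniform over those days; interval T of 59 to 62 days.

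Follow-up cycle day = ((d − 1 + T) mod L) + 1. The visit is outside the follicular phase if this exceeds L − 14.

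| L | Follicular days | Outside, T = 59 | T = 60 | T = 61 | T = 62 | Range | Baseline days that work at T = 61 |
|---|---|---|---|---|---|---|---|
| 26 | 12 | 7/12 | 8/12 | 9/12 | 10/12 | 58–83% | 1–3 |
| 28 | 14 | 3/14 | 4/14 | 5/14 | 6/14 | 21–43% | 1–9 |
| 30 | 16 | 1/16 | 0/16 | 1/16 | 2/16 | 0–12.5% | 1–15 |
| 35 | 21 | 11/21 | 10/21 | 9/21 | 8/21 | 38–52% | 10–21 |

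Example: for L = 28 and T = 61, 61 mod 28 = 5, so the cycle day moves forward by 5. Baseline days 10 to 14 then land on days 15 to 19, which is 5/14 = 36% outside. At L = 24, a length added as a check, no follicular baseline day works for any T from 59 to 62.

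**4. Collections with no phase rule.** If the baseline day is uniform over the whole cycle, the two collections fall in different phases in 6/28 to 12/28 (21–43%) at L = 28 and 14/26 to 20/26 (54–77%) at L = 26. In this model as many women move from follicular to luteal as the reverse, so the result is noise. If baseline is held follicular and follow-up drifts, every mismatch runs from follicular to luteal, and bias becomes possible.

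**5. Food log.** Even when the follow-up laboratory day is follicular at T = 61, the seven days before it can include up to 2 luteal days at L = 28 and up to 6 at L = 30.

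**6. Window.** With a 14-day luteal phase, the nearest follicular day is never more than 7 days away. At T = 61 the largest shift needed is 5 days at L = 28, 1 at L = 30, and 7 at L = 24, 26 and 35.

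**The case against.** The strongest reply is that this is largely unstated detail. Blood, blood pressure and BodPod may well be done on the laboratory day: the inpatient day belongs to the baseline measures, and Statistical Procedures sorts variables for analysis and does not set a calendar. That stands. For these three the timing is unstated, and the documents do not show that they are taken on another day. It does not rescue the food log or home sleep, which cannot be laboratory measures.

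A reader might infer that follow-up is fixed at exactly 2 months and that the team often cannot satisfy both rules. The documents do not support this. They give a nominal duration with no day count. One laboratory is named, and its staff already schedule baseline by phase and could choose a baseline day that works at every length in the table. The percentages assume that they do not. Only at the 24-day check does choice of day fail.

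A reader might also infer that the leptin result is biased or the sample size wrong. Neither follows. The documents give no cycle-phase effect on leptin, the stated purpose of the rule does not name leptin, blood pressure or body fat, and the figures above count phase mismatches without converting them into loss of power.

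**Conclusion.** The point holds in limited form. The rule does not cover the home food log or home sleep, which is a plain mismatch between its purpose and its wording. For blood, blood pressure and body composition the plan leaves phase open at both time points. For some women the 2-month follow-up and the follicular requirement may conflict, at the frequencies in the table, which depend on the assumed luteal length, baseline-day distribution and interval.

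The effect on the results cannot be sized: men and women aged 18 to 65 are eligible and the premenopausal share is not given. The targets of 17 and 25 stand. The missing window alone would be only a missing detail. What makes the change worthwhile is that it is cheap and protects paired change scores, including the one that sets the sample size.

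**What to change.** In Study participants, extend the rule to the fasting blood sample, blood pressure and BodPod by collecting them on arrival for the laboratory day (about 0900 h) at both visits. Place the 3-day food log in the same cycle phase at both time points where feasible. Record cycle day at every collection, and use it in a sensitivity analysis, for example by repeating the paired comparisons without phase-mismatched pairs.

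Experimental Procedures restricts end-of-treatment laboratory testing to compliant patients. The new wording should therefore not make blood, blood pressure or BodPod conditional on compliance where they would otherwise be collected; a phase-matched visit would serve.

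In Experimental Procedures, state one follow-up collection window, the same for CPAP and control participants. About ±7 days around day 61 suffices for the cycle lengths checked. The window must be reconciled with the treatment-phase length and with the compliance definition, which equates 70% of nights with 64 nights. That implies 64/0.70 = 91 nights, whereas 2 months has 59 to 62.

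The cost is protocol wording, tighter scheduling for premenopausal women and a small variation in follow-up time. The sample size does not change.
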